1. SYNOPSIS

Study Title	Operational evaluation of Mass Screening and Treatment using ultrasensitive rapid detection tests to reduce P. falciparum malaria incidence and prevalence in a malaria elimination program in Eastern Kayin State, Myanmar.	
Internal ref. no.	MAL 17011	
Study Design	Stepped wedge intervention	
Study Participants	Populations of villages with high P. falciparum incidence located in Eastern Kayin State, Myanmar.	
Planned Sample Size	60 villages (group 1) 60 villages (group 2)	
Planned Study Period	3 years	
	Objectives	Outcome Measures
Primary	To measure the impact of URDT-based MSAT on P. falciparum incidence at village-level (group 1 & 2)	Adjusted incidence rate ratio before/after MSAT
Secondary	1) To measure the impact of MSAT on prevalence of P. falciparum infection in malaria hotspots (group 1)	1) Prevalence of P. falciparum infection measured in the village by URDT and by reference method
	2) To measure the impact of reactive MSAT on incidence of seasonal malaria peaks / outbreaks (group 2)	2) Change in the incidence dynamics over the transmission season
	3) Feasibility of MSAT as a programmatic tool and as a reactive strategy (group 1 and 2)	3) Coverage of village population with intervention
	4) % of infections treated compared to infections detected by reference method (group 1 only)	4) % of P. falciparum positive samples by reference method which were positive by URDT and treated; % of P. falciparum negative samples by reference method which were positive by URDT and treated

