Figure 3: Average *P. falciparum* and *P. vivax* incidence in hotspots before and after MDA, centered on date of MDA. A marked decrease in *P. falciparum* incidence after MDA can be observed, in spite of an increase in incidence around 15 months after MDA. This increase is related to 5 hotspots (out of 52 followed up to M18) showing an incidence above 50 case/1000 for 1 month during the second year after MDA. This increase did not persist further.

In this project, we aim at an operational research deployment of URDT-based MSAT in the METF elimination program. This intervention will be tested in two types of setting, which correspond to two arms in this study. In group 1, MSAT will be used in a programmatic setting in order to decrease the reservoir of asymptomatic carriers in high incidence villages (following the same principles and objective as previously deployed MDA interventions). In group 2, we take advantage of the lighter framework of MSAT to use it as a reactive intervention in order to respond to malaria outbreaks in low to intermediate incidence villages. The MSAT intervention will be preceded with community-level consent and community engagement (CE) activities. MSAT will be conducted over a period of approximately 1 week in each hamlet, village or group of villages, and will consist in administering a *P. falciparum* URDT to all individuals agreeing to participate. A limited subgroup (expected 5-25%) will be found positive and receive supervised treatment over 3 days for the standard regimen (DP to cure asexual stage infection + single low-dose primaquine to destroy gametocytes). After this intervention, the incidence of clinical falciparum episodes will be monitored by the village MP. In group 1, a comparison of the prevalence at baseline and 12 months after MSAT intervention will be performed through a second URDT survey, in addition to which both baseline and 12-month surveys will include the collection of a 50 μ L capillary blood sample for reference detection in the laboratory.

The intervention will be evaluated primarily on its ability to reduce yearly cumulative incidence of clinical falciparum malaria compared to year before intervention. Additional evaluations of the impact of MSAT will include: in group 1, comparison of asymptomatic infection prevalence; and in group 2, modifications of the shape of the incidence curve following intervention.

Potential risks and benefits for participants

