9.2. The Number of Participants (group 1 only)

The sample size can be calculated for group 1 only, since the baseline cumulative incidence in group 2 will depend on surveillance outcomes, and often correspond to responses to a single case.

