9.3. Analysis of Outcome Measures

Primary outcome: stepped-wedge comparison of incidence.

The incidence comparison will be conducted over a 2-year series of weekly incidence data, corresponding to 12 months before and 12 months after MSAT intervention. A generalized additive multilevel mixed model will be used to adjust for location, season, and temporal trend due to MP activity using uni-(seasonality, duration of MP activity in the village) or bivariate (latitude and longitude) splines, including random intercept and slopes at village level. MSAT intervention will be included in the model as a 0-1 variable. The incidence rate ratio obtain for this variable will quantify the average decrease in incidence after MSAT campaign compared to before.

Secondary outcome: before-after comparison of prevalence

For each village, the fractional change in prevalence before MSAT and 12 months after will be calculated and compared to 0% change. This change will be compared to the fractional change observed after MDA.

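### The primary objective covers both groups, but section 9.3 gives one MSAT rate ratio and does not say how the groups enter the model; reactive MSAT has no planned rate ratio of its own

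*Combined protocol and SAP*

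**What the plan says.** The synopsis states the primary objective as the impact of URDT-based MSAT on *P. falciparum* "incidence at village-level (group 1 & 2"), with a single outcome measure, an adjusted before/after rate ratio. It plans "60 villages (group 1) 60 villages (group 2").

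Section 3 treats the groups as distinct: "This intervention will be tested in two types of setting, which correspond to two arms in this study". Group 1 is planned MSAT in villages with sustained high incidence. Group 2 is a reaction to outbreaks, or to a single case, where incidence is low to intermediate.

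Section 9.3 describes one model for the primary outcome, on weekly data "corresponding to 12 months before and 12 months after MSAT intervention". It adjusts for location, season and duration of malaria post activity, "including random intercept and slopes at village level". The effect is defined by two sentences: "MSAT intervention will be included in the model as a 0-1 variable", and "The incidence rate ratio obtain for this variable will quantify the average decrease in incidence after MSAT campaign compared to before". Neither mentions group.

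Section 9.2 says "The sample size can be calculated for group 1 only", because the group 2 baseline depends on surveillance and is often one case. Group 2 has a secondary outcome of its own in section 4, the duration and height of the seasonal peak.

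**The concern.** The two groups differ in how villages are chosen, in baseline incidence and in what MSAT is meant to achieve, so there is no reason to expect one common rate ratio. A single coefficient averages the two effects with weights set by case counts and the random-effect structure, not by the question. A useful reactive effect could be masked by a weak group 1 effect, or a group 1 effect could be carried over to reactive use. If the model is meant for group 1 alone, the primary objective for group 2 has no analysis that yields its stated outcome.

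**Working it through.** **The plan's own figure.** Section 9.2.1 gives the only sizing of the primary outcome: 60 villages in 6 waves, 190 inhabitants, size CV 0.49, ICC 0.12, 250/1000/year, alpha 0.01, power 0.90 (written as beta), detectable difference below 25/1000/year. I used the Hussey-Hughes stepped-wedge variance with 7 periods, an effective size of 190/(1 + 0.49²) = 153.2 per village-period, proportion 0.25 per period and two-sided alpha. The standard error is 0.00567, and (2.576 + 1.282) × 0.00567 = 0.0219, or 21.9/1000. This agrees with the plan when 0.25 is taken as the risk in each period; counting incidence per semester (0.125 per period) gives 33.4/1000/year. Either way the calculation concerns group 1 only.

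**Inputs for the weight of group 2.**
- Group 1 cases before, per village-year: 190 × 0.250 = 47.5 (section 9.2.1). With the baseline of the MDA villages in section 9.2.3, 190 × 0.125 = 23.75.
- Group 2 cases before: not given. Assumed 1 to 16 per village-year; 16 is 84/1000, the group 1 entry threshold, in 190 people.
- 60 villages per group (synopsis).
- True rate ratio for the weights: 0.5 in both groups (assumed).
- Random MSAT slope SD τ: 0 or 0.5 (assumed; section 9.3 does not say which variable the slope is on).

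**Formula.** The variance of a village's log ratio is 1/before + 1/after + τ². With equal numbers of villages, the share of group 2 is w₂/(w₁ + w₂), where w = 1/variance. This leaves out the splines of the planned model.

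Example, group 1 at 250/1000, 1 case in group 2, τ = 0: w₁ = 1/(1/47.5 + 1/23.75) = 15.83; w₂ = 1/(1 + 2) = 0.333; share = 0.333/16.17 = 2.1%.

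| Group 2 cases per village-year | Group 1 at 250, τ = 0 | Group 1 at 125, τ = 0 | Group 1 at 250, τ = 0.5 |
|---|---|---|---|
| 1 | 2.1% | 4.0% | 8.8% |
| 5 | 9.5% | 17.4% | 26.9% |
| 10 | 17.4% | 29.6% | 36.3% |
| 16 | 25.1% | 40.2% | 41.7% |

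With group 1 at 125, τ = 0.5 and 16 cases together, the share is 46.2%.

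**What the mixture does.** Take true ratios of 0.60 (group 1) and 1.00 (group 2). The pooled ratio is exp((1 − share) × ln 0.60).
- Share 2%: exp(0.98 × −0.511) = 0.61.
- Share 40%: exp(0.60 × −0.511) = 0.74.

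The weights change a little with the true ratios. Per village the Poisson information is ab/(a + b), with a cases after and b before. Group 1 at 250/1000 gives 47.5 × 28.5/76 = 17.8; group 2 with 1, 5 or 10 cases gives 0.5, 2.5 or 5. The shares are 2.7%, 12% and 22%, and the pooled ratios 0.61, 0.64 and 0.67. With group 1 at 125/1000 and 10 cases in group 2, the share is 5/(8.9 + 5) = 36% and the pooled ratio 0.72. Total cases after over total before gives nearly the same, for example (28.5 + 10)/(47.5 + 10) = 0.67.

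**What separate estimates would give.** For group 2 alone (60 villages, true ratio 0.5, Poisson error only), 1 case per village-year gives SE(log) = √(3/60) = 0.224 and a 95% interval of 0.32 to 0.78. Five cases give SE = √(0.6/60) = 0.100 and 0.41 to 0.61. Variation between villages would widen both.

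**The case against.** The strongest reply is that section 9.3 never says both groups go into one fit. Its heading speaks of a stepped-wedge comparison, the matching sizing section is limited to group 1, and waves are described only for group 1. It can be read as group 1 only, as one fit per group, or as pooled. The text of section 9.1 also breaks off where it turns to adjusted estimates. This stands: pooling is a possible reading, not a stated plan. It does not remove the problem. A group-1-only fit gives no rate ratio for group 2. A fit per group would be sound but is not written down. The secondary outcome for group 2 describes the peak and is not a rate ratio.

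A reader might infer that a pooled ratio would be almost entirely the group 1 effect. That needs group 2 counts of about 1 or 2 per village-year and little or no random MSAT slope. Group 2 also takes outbreak villages and clusters of villages, and section 9.3 does plan village slopes; if one is on MSAT, the weights move towards equality. Clusters of a few houses pull the other way. The documents do not fix the share.

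A reader might also infer that the trial would publish the single ratio as the effect of reactive MSAT. No section says so; section 9.3 calls it an average.

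**Conclusion.** The concern holds as a gap between the primary objective and the primary analysis. Followed as written, section 9.3 yields no rate ratio for reactive MSAT: one common coefficient is a mixture, and a group 1 fit leaves group 2 out. Under pooling, group 2 carries about 2% to 40% of the weight (46% in the most extreme combination in the working), and true ratios of 0.60 and 1.00 appear as about 0.61 to 0.74. These sizes rest on assumed group 2 counts, assumed true ratios, an assumed slope SD and a simplification of the planned model. The conclusion does not depend on where in the range the weight falls: even at 40%, an absent reactive effect is reported within an apparent 26% reduction. The documents support neither a claim that pooling is planned nor one that group 1 decides the result almost alone.

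**What to change.** In section 9.3, replace the single MSAT term with an MSAT-by-group term (and a group main effect), or fit the model separately in each group. Report one rate ratio with its interval per group. State that only the group 1 ratio is backed by the sample size in section 9.2.1. Any pooled ratio should be supplementary and not read as the effect of reactive MSAT. Group-specific curves for season and malaria post duration are optional; separate fits give them automatically.

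The cost is wording in the analysis section, with no new data. The group 2 interval may be wide, as the working shows at 1 case per village-year, but it reflects what the study can say about reactive use.

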4. OBJECTIVES AND OUTCOME MEASURES

Objectives	Outcome Measures	Timepoint(s) of evaluation of this outcome measure (if applicable)
Primary Objective To measure the impact of URDT-based MSAT on P. falciparum incidence at village-level.	Adjusted incidence rate ratio before/after MSAT	Follow-up from MP opening to end of study
Secondary Objectives 1) To measure the impact of MSAT on prevalence of P. falciparum infection in malaria hotspots	1) Prevalence of P. falciparum infection measured in the village by URDT and by reference method (group 1)	1) Comparison between M0 survey (during MSAT) and M12 survey (12 months after)
2) To measure the impact of reactive MSAT on incidence of seasonal malaria peaks / outbreaks.	2) Change in the incidence dynamics over the transmission season (group 2)	2) Duration and height of seasonal peak before, during and after reactive intervention
3) Feasibility of MSAT as a programmatic tool and as a reactive strategy.	3) Coverage of village population with intervention	3) coverage based on census conducted before/during MSAT
4) % of infections treated compared to infections detected by reference method	4) % of P. falciparum positive samples by reference method which were positive by URDT and treated; % of P. falciparum negative samples by reference method which were positive by URDT and treated (group 1)	Group 1 only
Tertiary Objectives Retrospective comparison of MSAT versus MDA on prevalence and incidence of P. falciparum malaria	Cumulative incidence of falciparum malaria episodes before and after MDA/MSAT; prevalence of falciparum infection before and after MDA/MSAT	Entire incidence series

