9.2.2.2. Number of villages required for prevalence comparison

We assume an average *P. falciparum* prevalence of 16% in group 1 villages using reference assay. Before/after comparison at village level will use samples from the same village but not necessarily the same individuals (correlation between paired observations set to 0). The sample size was calculated assuming 60 samples per cluster (the minimal number of samples collected at M12), an intra-cluster correlation coefficient of 0.15, the sample size required to identify a 50% decrease 12 months after intervention compared to baseline is 43 clusters for alpha=0.05 and 1-beta=0.8.

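### Section 9.3 analyses the before/after prevalence outcome only as a fractional change per village, with no rule for combining villages, although 9.2.2.2 sizes it as a clustered comparison of two proportions

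*Combined protocol and SAP*

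**What the plan says.** Section 4 makes *P. falciparum* prevalence in group 1, by URDT and by the reference method, the first secondary outcome, comparing M0 with M12.

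Its analysis in section 9.3 is two sentences. The first is "For each village, the fractional change in prevalence before MSAT and 12 months after will be calculated and compared to 0% change". The second is "This change will be compared to the fractional change observed after MDA". The mixed model in the same section is for incidence only, and no other section gives an estimator for prevalence.

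Two sections size this outcome. Section 9.2.2.1 sets each village's M12 sample by confidence-interval width and expects 60 to 120 samples. Section 9.2.2.2 sets the number of villages. It assumes "prevalence of 16% in group 1 villages using reference assay", 60 samples per cluster, "an intra-cluster correlation coefficient of 0.15" and zero correlation between paired observations, and concludes that "the sample size required to identify a 50% decrease 12 months after intervention compared to baseline is 43 clusters for alpha=0.05 and 1-beta=0.8".

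**The concern.** The fractional change is M12 prevalence divided by M0 prevalence, minus 1. It has no value when M0 has no positives, stops at -100% below and is open above. A village with 2 baseline positives produces the same kind of figure as one with 40, with far more noise.

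The objective concerns the impact of MSAT across group 1, so the village figures must at some point be combined, and section 9.3 does not say how. On a skewed, noisy ratio the mean, the median and the pooled change answer differently. The reported size of the fall, and the contrast with MDA, would then depend partly on a choice made after the data are seen and on how many villages had few baseline positives. The power claimed in 9.2.2.2 also belongs to a different analysis.

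**Working it through.** **Inputs from the documents.** Section 9.2.2.2: 16% falling to 8%, 60 per cluster, ICC 0.15, alpha 0.05, power 0.80, paired correlation 0. Section 9.2.1: 60 villages, mean size 190, coefficient of variation 0.49. Appendix D (sensitivity/specificity): field uRDT 39.6%/99.3%, Quansys 83.0%/96.1%.

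**Assumptions not in the documents.** Beta-distributed village prevalence; 80% of each village tested at M0; up to 90 tested at M12; log-SD 0.3 for variation in village change; the t-test and signed-rank test as candidate analyses.

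**1. The plan's own figure.** Two-sided, pooled variance:

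n = [1.960 x sqrt(2 x 0.12 x 0.88) + 0.842 x sqrt(0.16 x 0.84 + 0.08 x 0.92)]^2 / 0.08^2 = 258 per period.

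Design effect = 1 + 59 x 0.15 = 9.85. Clusters = 258 x 9.85 / 60 = 42.4, so 43. The figure reproduces exactly, as a comparison of proportions.

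**2. Instability.** Take 150 tested at M0 and 60 at M12. With 2 baseline positives, each M12 positive moves the village's figure by (1/60)/(2/150) = 125 percentage points. With 40 baseline positives it moves it by (1/60)/(40/150) = 6 points. An unweighted summary treats the two villages alike.

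**3. Undefined villages.** If measured prevalence is beta with mean 0.16 and ICC 0.15, then a = 0.16 x 0.85/0.15 = 0.907, b = 0.84 x 0.85/0.15 = 4.76, and P(no positives among m) = B(a, b+m)/B(a, b). This gives 9.3% at m = 60, 4.2% at 150 and 3.4% at 190. At ICC 0.05 it is 1.0%, 0.1% and 0.05%.

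Applying Appendix D accuracy to a true prevalence of (0.16 - 0.039)/(0.83 + 0.961 - 1) = 15.3%, with 150 tested and ICC 0.15, gives 3.7% by field URDT (2.2 of 60 villages) and about 0.01% by Quansys, whose false positives make a zero count rare. With village size varying and 80% tested, the shares are about 5% by field URDT and 0.2% to 0.3% by Quansys.

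**4. Summaries when village prevalence persists.** Simulation of 60 villages, ICC 0.15. The reference rows take 16% as what the assay shows, without further misclassification.

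| Setting | Mean | Median | Pooled |
|---|---|---|---|
| No change, field URDT | +14% | -5% | 0% |
| No change, reference | +8% | near -5% | 0% |
| 50% fall, field URDT | -32% | -48% | -45% |
| 50% fall, reference | -46% | -54% | -50% |

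The URDT pooled value of -45% is not a fault of the pooling. Measured prevalence goes from 0.396 x 0.16 + 0.007 x 0.84 = 6.9% to 0.396 x 0.08 + 0.007 x 0.92 = 3.8%, a fall of 45%. The estimator's own error by URDT is therefore the gap between -32% and -45%.

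With no true change, a t-test rejects in about 11% of runs by URDT and 7% by reference; a signed-rank test rejects in 5.7% and 4.9%. With a true 50% fall, t-test power is 83% to 99% across assays and ICCs of 0.15 and 0.05, and signed-rank power is above 99%.

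**5. Sensitivity to before/after correlation.** With 43 villages, 60 per survey, ICC 0.15, no misclassification and village prevalence redrawn independently at M12, a true 50% fall gives a mean village change of about +5% to +12%, a median of -73% and a pooled change of -49%. A t-test on village differences then has 81% power, in line with the stated 80%; a t-test on fractional changes has 10%. With no true change the mean is about +120% against +2% pooled.

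**The case against.** The strongest reply is that section 9.3 names no mean, median, equal weighting or t-test. Read literally it is a village-by-village comparison, and section 9.2.2.1 sizes the M12 survey for one. That stands: village results are a legitimate display, and the t-test figures describe an analysis that the plan does not commit to. It does not remove the gap, because 9.2.2.2 sizes a comparison across villages and 9.3 gives no way to make it.

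Three stronger readings are tempting, and the documents do not support them.

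- *Every summary gives a wrong answer.* A signed-rank test on the same figures stays near 5% when village prevalence persists. The mean's bias is upward, which works against declaring MSAT effective.
- *Many villages drop out on both assays.* The problem is largely confined to URDT. Group 1 villages are also selected for more than 84 cases/1000/year, so a beta distribution peaking at zero, as ICC 0.15 implies, may overstate it.
- *The real power is 10%.* That requires zero correlation between a village's two surveys and 60 baseline samples. Section 9.2.2.2 sets the correlation to 0 because individuals may differ, and the whole village is invited at baseline. With full persistence the fractional-change t-test has 97% to 98% power.

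**Conclusion.** The concern holds as a weakness of the estimator and a gap in the specification of a secondary outcome. The 43 clusters are correct, but for a clustered comparison of proportions that section 9.3 does not carry out.

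The size depends on the before/after village correlation, which the documents do not establish. If village prevalence persists, a true 50% fall is still usually detected, but the unweighted mean by URDT is 13 points too small (-32% against -45% pooled) and mean and median differ by 16 points. By reference assay the spread is smaller (-46% to -54%). If the correlation is near 0, the mean can have the wrong sign. Undefined villages are the lesser issue: about 3 of 60 by field URDT (5% x 60) and fewer than 1 by Quansys. These figures rest on the assumptions listed in the working, chiefly the beta distribution with ICC 0.15 and 80% baseline coverage. A reader should not infer that the plan has specified an invalid test; it has specified none.

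**What to change.** In section 9.3, define the group 1 before/after estimate as a prevalence ratio (M12 to M0) with 95% CI from one clustered binomial model on all M0 and M12 results, fitted separately for URDT and for the reference assay. Include a period term, a village random intercept and a village random period effect.

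State how the ratio is obtained, since a logit mixed model gives a conditional odds ratio by default. Options are a log link, marginal standardisation from the logit model, or GEE with robust standard errors (a marginal alternative without the random effects). All of them keep villages with zero counts, take account of the amount of data per village, and match the comparison sized in 9.2.2.2.

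Keep village fractional changes as a descriptive table or plot, marking those with no baseline positives as not calculable.

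Compare with MDA through the ratio of the two prevalence ratios, only where MDA villages have prevalence data by a comparable assay. The documents do not show that they were surveyed by URDT or Quansys, so this must be confirmed first.

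The cost is a change of SAP wording and slightly more modelling. No new MSAT data are needed.
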